Letrozole dose will be increased in subsequent cycles in both groups based on ovulatory response in stairstep fashion (details within protocol). Maximum letrozole dose will be 7.5 mg a day for 5 days.

Study Duration: 2 years

[figure not shown]
Subject **Participation Duration:**

Approximately 15 weeks of active participation time. Clinical chart abstraction and remote follow up will be continued until 6-8 weeks post-delivery in pregnant women.

Complete **Enrollment:**

Estimated Time to 20 months with 3 months follow up for final enrollees. 21 months by enrolling ~ 10 women per month across the 4 sites.

Schematic of Study Design:

Revised from PPCOS II Trial protocol study diagram

Detailed Schematic of Study Design:

Х

Obtain informed consent. Screen potential participants by inclusion and exclusion Screening Visit criteria; obtain history, physical exam. Pre-conception counseling. Progestin withdraw if indicated. Total: 184 Confirm negative pregnancy test, dispense meds, dispense and review Baseline journal log Visit (Cycle day 1-3, random start) Randomize Arm 1:92 Letrozole Arm 2:92 Letrozole + 50mg participants CC Participants to take Letrozole 2.5 + 1 pill study medication daily cycle days 3-5, Cycle day Participants to complete journal log and other assigned questionnaires 3-7 Repeat Perform midluteal assessments (transvaginal ultrasound, progesterone lab draw, cycles at Midluteal visit review journal log). adjusted Cylce day 18- 26 letrozole dosing as Progesterone < 3ng/mL needed Progesterone ≥ 3ng/mL Progesterone < 3ng/mL & no follicular up to 3 Participant awaits & follicular development development. Increase cycles menses and pregnancy Repeat progesterone in Letrozole dose by test at 2 wks) 10-14 days 2.5mg/day up to maximum dose of 7.5mg/day starting that day Progesterone ≥ 3ng/mL Increase Letrozole dose by 2.5mg/day up to maximum dose of 7.5mg/day starting with next Menses check in menses) Menses onset No menses: within two Menses onset. Confirm weeks - urine negative home pregnancy test pregnancy test prior to initiating new cycle Positive → serum Negative → Proceed with next cycle hCG confirmed: Move to Pregnancy follow up track

вазед оп NIDCR Clinical Trial (Interventional) Protocol Template v4.0 - 20140103

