4 STUDY DESIGN

4.1 Treatment Design

This will be a multicenter, open trial of oral letrozole versus combination of oral letrozole and clomiphene citrate for the treatment of infertility in patients with oligo-ovulation or anovulation. Patients will be randomized to one of two treatment arms, to receive either an initial dose of letrozole 2.5 mg alone or clomiphene citrate 50 mg and letrozole 2.5 mg for 5 days during their menstrual cycle. Letrozole dosing will be escalated in a stair-step fashion based on ovulation results. Max dose of letrozole will not exceed 7.5 mg.

Participation in active treatment will last for up to 3 treatment cycles, approximately up to 15 weeks. Participants will be monitored at monthly intervals during expected mid-luteal phase to evaluate response to medication by evaluating ultrasound and progesterone parameters.

The dose will be adjusted according to response at mid-luteal visit.

- Anovulatory progesterone level < 3 and no evidence of follicular development and corpora lutea → increase letrozole dose on that day. This would be considered start of new treatment cycle (CD3).
- Anovulatory progesterone level < 3 with evidence of follicular development (follicle ≥14 mm) → repeat progesterone level based on LH testing (6-8 days following positive) or at 2 weeks if no positive → increase dose at menses visit (2nd progesterone is ovulatory) or increase dose at time of second progesterone if level < 3.

- Progesterone level ≥3 → maintain same dose for next treatment cycle

Anytime ovulation induction medication is started, pregnancy test to be performed prior to initiation of new treatment cycle.

Randomization will be stratified by site, age (< 35 versus \geq 35) and BMI (< 30 and \geq 30) to ensure similar comparison groups in these characteristics that highly impact outcomes. Randomization will be via a computer based central randomization to ensure adequate allocation concealment.

Enrollment will take approximately 20 months if ~ 10 subjects are enrolled per month. Active subject participation will be through completion of 3 cycles. We will follow up with patient regarding pregnancy and delivery outcomes.

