- 4. Collect and review journal logs (side effects, menstrual logs, intercourse log, concomitant medications, completion or missing entry)
- 5. Count medication and confirm contact method for informing participant of plan based on lab and pregnancy test at end of cycle.
- 6. Medication dispensed for next cycle or patient may return on CD1-3 (preferable if able).

Instructions based on progesterone level and ultrasound results:

- Progesterone level ≥ 3 ng/mL → instruct participant to await menses and perform pregnancy test with menses or if no menses, perform pregnancy test 2 weeks after midluteal visit.
- 2. Anovulatory progesterone level < 3 ng/mL and with evidence of follicular development (mean follicle size ≥ 14 mm → repeat progesterone level in 10-14 days.
 - a. If repeat (2nd P4) is ovulatory progesterone level ≥ 3 ng/mL → increase treatment dose next cycle with menses after negative pregnancy test
 - b. If repeat (2nd P4) is anovulatory progesterone level < 3 ng/mL → increase treatment dose and initiate next cycle after negative pregnancy test.
- 3. Anovulatory progesterone level < 3 ng/mL and no evidence of follicular development or corpora lutea → increase ovulation medication on that that day after negative pregnancy test. This is considered the start of a new cycle. Next mid-luteal clinic visit would be scheduled for 7-8 days following positive LH test or 18 to 26 days following initiation of medication.

Menses check in appointment (via RedCap)

This check in is necessary in order to initiate next cycle. At onset of menses, each participant will take a home pregnancy test and complete the RedCap form indicating "Negative Pregnancy test". If no menses within 2 weeks after the midluteal visit, participants will take a pregnancy test.

- If positive urine pregnancy test, lab visit scheduled for serum hCG level and repeat in 48-72 hours.
- o If negative urine pregnancy test, start medication on Cycle day 3 of menses
- Submit journal logs via email or in person

Pregnancy lab Visits (part of standard of care)

- If positive urine pregnancy test, lab visit scheduled for serum quantitative hCG level and repeat in 48-72 hours.
- Appropriate rise:
 - 2 day rise multiply level x 1.7
 - o 3 day rise multiple level x 2.3
 - 4 day rise multiply level x 2.89
- If appropriate rise, schedule Transvaginal ultrasound at 6 to 7 weeks and visit with provider.

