7.3 Intermediate Visits

Participants will return for a midluteal study visit on cycle day 21-24 or 7-9 days following positive ovulation prediction test to determine if ovulation occurred. This visit will include an ultrasound and a progesterone lab.

If there is no ovulation, the daily dose of letrozole will be increased by 2.5 mg, to begin immediately. During the first cycle after letrozole dose increase, participants would receive 5mg daily for 5 days. If participants receive a second letrozole dose increase, they would receive 7.5 mg Letrozole daily for 5 days. The maximum dose for Letrozole in this study is 7.5 mg. CC 50 mg will be given on the same days as the letrozole in all cycles in the combination arm. Midluteal visits will be performed in all cycles. Each participant will complete a maximum of 3 cycles of medical therapy. On average we expect this to be about 4 months time, however, delayed ovulation, a biochemical pregnancy, or 1st trimester pregnancy loss in the first or second treatment cycle could delay the start of subsequent cycles, and therefore would extend active participation.

Cycle 1 Midluteal Visit

Timing will be based on LH testing, ideally around 7-8 days post-positive test or CD21-24 if no positive test

- Transvaginal ultrasound to assess for corpora lutea and endometrial thickness and pattern
- Serum progesterone assessment for ovulation
- Review subject calendar log and record adverse events as reported by subject or observed by investigator.
- Determine dosage for next cycle based on ultrasound and progesterone results and record in RedCap
 - If there is no ovulation, the daily dose of letrozole will be increased by 2.5 mg (5mg). The combination arm will continue to receive CC 50mg along with the increased letrozole dose.
 - If there is ovulation, treatment will be repeated in the next cycle with the same dose of letrozole. The combination arm will continue to receive CC 50mg along with letrozole 2.5mg.
- Schedule a follow up Progesterone lab if necessary
 - Participants with anovulatory progesterone levels (<3 ng/ml) and evidence of follicular development will return for a repeat progesterone level assessment in 10-14 days.
 - Participants with elevated anovulatory progesterone levels (1.5 < P4 < 3.0) and corpus luteum on ultrasound will return for a repeat progesterone level assessment in 2-3 days

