- Dispense pregnancy test and medication for next cycle and review instructions for medication (dispense medication if unable to return to pick up meds, if can easily return, have participant return for med pick up)
 - Participants without ovulation nor evidence of follicular development are to complete pregnancy test and begin medication at new dose immediately following negative pregnancy test
 - Participants with ovulation are to wait until onset of menses, or two weeks after midluteal visit to complete pregnancy test. They can begin medication at same dose following negative pregnancy test. Participants with a positive pregnancy test will be moved to pregnancy track and will return dispensed medication at their next study visit.

- Collect any unused medication from current cycle and document participant compliance in RedCap
- Record results of ultrasound and serum progesterone in RedCap

Cycle 1 Follow-up Midluteal Visit*

Participants with anovulatory progesterone levels (<3 ng/ml) and evidence of follicular development at their midluteal visit will return for a repeat progesterone level assessment in 10-14 days. This can be performed at a local lab if the participant prefers.

- Serum progesterone assessment for ovulation
- Review subject calendar log and record adverse events as reported by subject or observed by investigator.
- Review instructions for previously dispensed medication/dispense medication if not yet dispensed
 - Participants without ovulation are to complete pregnancy test and begin medication at new dose following either a spontaneous menses or withdraw bleed and a negative pregnancy test. They can begin taking medication to induce a withdraw bleed on cycle day 35, following a negative pregnancy test.
 - Participants with ovulation are to wait until onset of menses, or two weeks after midluteal visit to complete pregnancy test. They can begin medication at new dose following negative pregnancy test (if ovulation did not occur on or before cycle day 21). Participants with a positive pregnancy test will be moved to pregnancy track and will return dispensed medication at their next study visit.
 - Participants who were initially anovulatory at a study visit prior to cycle day 21, who are ovulatory at a follow up visit by cycle day 21 will be maintained on the same dose of medication. This may occur if participant's study visit was moved up due to an early false positive ovulation prediction test.

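### The 7.3 dispensing bullets and the schematic drop the no-corpora-lutea condition that 4.1 and 4.2 set for a same-day letrozole increase (minor)

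*Combined protocol and SAP*

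**What the plan says.** Section 4.1 ties a same-day letrozole increase to a progesterone below 3 with "no evidence of follicular development and corpora lutea". Section 4.2 gives the same rule with clearer wording, "no evidence of follicular development or corpora lutea", and adds a negative pregnancy test. Both sections count that start as a new treatment cycle. Section 4.1 spells out what follicular development means: "evidence of follicular development (follicle ≥14 mm". Corpora lutea are listed separately from it.

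Section 7.3, which sets out the visits, instructs under both the Cycle 1 and the Cycle 2 Midluteal Visit: "Participants without ovulation nor evidence of follicular development are to complete pregnancy test and begin medication at new dose immediately following negative pregnancy test". Corpora lutea are not mentioned. The detailed schematic in the Protocol Summary likewise pairs a progesterone below 3 with absent follicular development and raises the dose by "2.5mg/day up to maximum dose of 7.5mg/day starting that day".

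Section 7.3 does deal with a corpus luteum in one situation. When progesterone lies between 1.5 and 3.0, women with a "corpus luteum on ultrasound will return for a repeat progesterone level assessment in 2-3 days". No instruction covers a corpus luteum with progesterone of 1.5 or below.

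**The concern.** The same scan and blood result can lead to two different actions, depending on which section the staff member follows. Someone working from 4.1 or 4.2 finds that the condition for same-day dosing is not met and finds no other branch. Someone working from the 7.3 bullet starts the next course, with clomiphene as well in the combination arm.

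A corpus luteum suggests that ovulation may have happened recently. Where ovulation is accepted, the protocol puts off the pregnancy test until menses or two weeks after the midluteal visit. Under the 7.3 bullet the test is done before an immediate start, when a negative result says little about a conception in that cycle. At stake, then, is uniform dosing across four sites and not starting ovulation induction straight after a possible ovulation.

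**Working it through.** No figure in the plan underlies this point, so the main check is a comparison of the rules.

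**Can the missing condition be read into 7.3?**
- Not through the word ovulation. Section 3.1.1 defines it by progesterone alone, and 7.3 itself describes progesterone between 1.5 and 3.0 with a corpus luteum as anovulatory.
- Not through follicular development. That is a follicle of 14 mm or more, and 4.1 and 4.2 name corpora lutea as a separate item.

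**Rules side by side, for women with no follicle of 14 mm or more**

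| Progesterone (ng/mL) | Corpus luteum | 4.1 and 4.2 | 7.3 bullets, cycles 1 and 2 |
|---|---|---|---|
| below 3 | no | raise dose that day | raise dose at once |
| 1.5 or below | yes | condition not met; no other branch | raise dose at once |
| above 1.5, below 3 | yes | condition not met; no other branch | specific rule: repeat in 2-3 days (the dispensing bullet, read alone, says start) |
| 3 or above | either | await menses, same dose | await menses, same dose |

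Only the second row has no rule that settles it. The cycle 3 visit is unaffected because no further course follows it.

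**How many visits could be involved**

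Inputs: 92 women per arm (5.1). Letrozole ovulation is 49.4% in cycle 1 and 64.2% in cycle 2 (PPCOS II table, 12.1.1). Pilot ovulation is 43% on letrozole and 77% on the combination (2.1, Preliminary Data). Assumptions: all 92 women per arm reach cycle 2, and the pilot's single-cycle combination rate is carried forward to cycle 2.

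Expected visits with a first progesterone below 3 = 92 × (1 − ovulation rate):
- Cycle 1, letrozole: 92 × 0.506 = 46.6 (PPCOS II) or 92 × 0.57 = 52.4 (pilot).
- Cycle 1, combination: 92 × 0.23 = 21.2.
- Cycle 1 total: 67.7 to 73.6.
- Cycle 2, letrozole: 92 × 0.358 = 32.9. Combination: 21.2. Total: 54.1.
- Both cycles: 121.8 to 127.7.

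The share of these visits in the second row is not in the documents. Assumed values give:
- 0%: 0 visits.
- 1%: 1.2 to 1.3 visits.
- 5%: 6.1 to 6.4 visits.

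**The case against.** The best defence is that 7.3 is coherent on its own. It considers the corpus luteum, sets a cut-off at 1.5, and asks for a repeat only above it. The complement would be that at 1.5 or below a corpus luteum does not delay treatment, which fits the progesterone-only definition of ovulation and the aim in 4.1.1 of keeping treatment moving. That may be what the investigators intended, but 7.3 does not say so, and 4.1 and 4.2 both name corpora lutea as a condition. If it was the intention, those two sections would need changing; the text does not agree as it stands.

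Several other objections stand and limit the point:
- A reader might infer that 4.1 and 4.2 forbid dosing with a corpus luteum. They do not say so. They make its absence a condition and are otherwise silent, so withholding is only implied.
- A reader might infer a second conflict between 1.5 and 3.0. The 2-3 day repeat rule sits in the same visit list and is the more specific instruction; it governs.
- A reader might count the lost treatment cycle or the higher dose as harm. The next course uses one of the three cycles whenever it starts, and a late ovulatory progesterone generally leads to an increase as well, apart from the day-21 exception in 7.3. Mainly the timing differs.
- A reader might extend the criticism to the random-start rule in 4.2 and 7.1, which also relies on progesterone and follicular development only. That is a consistent rule for entry to the trial and contradicts nothing.
- The schematic's text is scrambled by extraction, and a diagram may abbreviate. The two bullets carry the point.

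**Conclusion.** The plan is wrong as written on this detail, and the matter is minor. The 7.3 bullets for cycles 1 and 2, and the schematic, omit a condition that 4.1 and 4.2 set. This leaves one combination of findings for which 7.3 says start now and 4.1 and 4.2 give no authority to do so.

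The number affected is probably very small and may be zero. The range of 0 to about 6 visits rests on an assumed share of 0% to 5% and on a ceiling that ignores pregnancy and dropout before cycle 2.

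A reader might infer that the primary result is at risk; the documents do not support that. Section 3.1.1 uses the first progesterone of each cycle. It does allow a better-timed value to replace a mistimed one, and immediate dosing could mean that no such value is taken. With so few visits and an outcome cumulated over up to three cycles, the effect is negligible.

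**What to change.** - Add *and no corpora lutea* to the dispensing bullets under the Cycle 1 and Cycle 2 Midluteal Visits in 7.3, and to the matching box in the schematic.
- Add one line to 4.1, 4.2 and 7.3 for a corpus luteum with progesterone of 1.5 or below: do not dose that day, and repeat progesterone at the 2-3 day interval that 7.3 already uses. Then follow the branches that 4.2 already gives for a second progesterone. Below 3, start the increased dose after a negative pregnancy test; at 3 or above, wait for menses. The day-21 exception in 7.3 stays.
- For progesterone between 1.5 and 3.0, a cross-reference from the dispensing bullet to the 2-3 day repeat rule is enough.
- Leave the random-start rule alone.

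The scan already supplies the finding, since the visit includes "Transvaginal ultrasound to assess for corpora lutea and endometrial thickness and pattern". The cost is a small text amendment, plus an extra progesterone draw and a few days' delay for very few women, possibly none.

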3.1.1 Primary Outcome Measure

The primary outcome measure is the occurrence of ovulation during the study period. Ovulation is defined as a mid-luteal progesterone level > 3 ng/mL. This will be tested 6-8 days following the patient reporting of an LH surge. If no LH surge is detected the lab will be drawn on cycle day 21-24. We will also analyze the ovulation rate of the follow up progesterone level.

We will utilize an intent-to-treat approach for the primary analysis of ovulation rate (utilizing the first progesterone level of each cycle) within the two treatment arms. If it is determined that timing of the initial progesterone level is inaccurate based on LH testing or patient symptoms, the progesterone test that is most clinically in line with accurate timing (6-8 days post LH surge) will be used. Ovulation rate will also be reported in those with a delayed response to treatment (needed repeat progesterone level due to anovulatory mid-luteal P4 level and follicle ≥ 14 mm). Patients will be analyzed according to the treatment group to which they are assigned, even if they did not receive the intended treatment or received only a portion of it. We will also perform a per protocol analysis to include only those patients who initiate treatment. Thus, those that are randomized but do not take the treatment due ineligibility will be excluded from the per protocol analysis. This per protocol analysis will provide data that is helpful to clinicians as it will include only those who initiated treatment.

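### For women ovulatory only on the repeat progesterone, 7.3 allows the next course without menses, after a home pregnancy test that may come too early

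*Combined protocol and SAP*

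**What the plan says.** The point concerns women whose first progesterone in a cycle is below 3 ng/mL, who have a follicle of at least 14 mm, and whose repeat progesterone is 3 ng/mL or more.

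- **7.3, Follow-up Midluteal Visit (cycle 1).** Women with ovulation wait until menses starts "or two weeks after midluteal visit to complete pregnancy test. They can begin medication at new dose following negative pregnancy test". Cycle 2 has the same rule in nearly the same words, and the Menses Check-In entries for both cycles repeat it. No bleed is made a condition.
- **4.2, item 2a.** After an ovulatory repeat, the instruction is to "increase treatment dose next cycle with menses after negative pregnancy test".
- **4.2, menses check-in.** "If negative urine pregnancy test, start medication on Cycle day 3 of menses". For the woman who does not bleed, it orders only a test: "If no menses within 2 weeks after the midluteal visit, participants will take a pregnancy test". It does not say that she may start.
- **4.1.** The instruction is to "increase dose at menses visit (2nd progesterone is ovulatory"). This fits 4.2, though a menses visit could also be a check-in held without menses.
- **Detailed schematic.** The box for an ovulatory repeat appears to tie the dose increase to the next menses. The general check-in box, for women without menses, reads "Negative → Proceed with next cycle".
- **Appendix A.** The monthly midluteal visit and the follow-up midluteal visit have separate columns. The check-in is timed from menses or two weeks after the midluteal visit.

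**The concern.** The plan excludes current pregnancy and requires a pregnancy test before each start of medication. For late ovulators, two drafting gaps can combine to weaken that safeguard: 7.3 does not require a bleed, and the two-week clock has no stated starting visit.

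If a site counts from the first visit, the test may precede the time at which a conception from the late ovulation can be detected. Letrozole at a raised dose, with clomiphene in the combination arm, could then be started in early pregnancy.

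Little else would catch the error. The test is a home urine test, and serum hCG follows only a positive result (8.2.1). The check-in can be remote, and the next course may already have been dispensed (7.3).

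The rule is also looser than its neighbours. At the cycle 1 follow-up visit, women who have not ovulated must have a spontaneous or induced bleed before restarting. A random start at baseline is allowed only once recent ovulation is excluded (4.2, 7.1).

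**Working it through.** The plan gives no figure of its own here. The check is a comparison of texts, then day counts from the plan's own intervals.

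**Which visit starts the two weeks?** Two features favour the first visit. In the follow-up entry, 7.3 uses *midluteal visit* for the visit at which the follicle was seen, and Appendix A separates the two visits and times the check-in from the midluteal visit. Two features favour the follow-up visit. The sentence sits under that visit's heading, and 7.3 remarks that delayed ovulation can delay later cycles. The plan does not decide between them.

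**Inputs**
- D, days from first visit to repeat draw: 10 to 14 (4.2 item 2; 7.3). The separate short recall, for progesterone between 1.5 and 3.0 with a corpus luteum, is at 2 to 3 days (7.3).
- Interval from anchor visit to test: 14 days.
- S, days from first visit to LH surge, with S ≥ 0 when the surge follows that visit.
- p, days from surge to a draw timed by LH test: 6 to 8 (3.1.1: "This will be tested 6-8 days following the patient reporting of an LH surge"); 7.3 gives 7 to 9 for the first visit.

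**First-visit anchor, repeat at 10 to 14 days**
- Test minus draw = 14 − D: 14 − 10 = 4, and 14 − 14 = 0. So 0 to 4 days.
- Test minus surge = 14 − S, which is at most 14 days for any surge after the first visit. A surge shortly before the first visit would make this longer and the test safer.

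**First-visit anchor, repeat timed by LH test.** Section 4.1 also allows "repeat progesterone level based on LH testing (6-8 days following positive) or at 2 weeks if no positive". If the draw, at S + p, falls by day 14, then S ≤ 14 − 6 = 8. Test minus surge is 14 − 8 = 6 to 14 − 0 = 14 days. Test minus draw is 14 − S − p: 14 − 8 − 6 = 0 to 14 − 0 − 6 = 8 days.

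**Follow-up anchor**
- Test minus draw = 14 days. Test minus first visit = D + 14 = 24 to 28 days.
- The two readings therefore differ by D, that is 10 to 14 days. With a first visit on cycle day 21 to 24, the test falls on day 35 to 38 (first-visit anchor) or day 45 to 52 (follow-up anchor).

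**Groups not exposed to the early test**
- Ovulatory at the first visit: 6 + 14 = 20 to 9 + 14 = 23 days after the surge.
- Short recall, first-visit anchor: 14 − 3 = 11 to 14 − 2 = 12 days after the draw. If that draw was 6 to 8 days after the surge, this is 6 + 11 = 17 to 8 + 12 = 20 days after it.

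**When is the test too early?** The documents give no detection limit for a home urine test. Assume that it is reliable from R = 10, 12 or 14 days after ovulation, and take ovulation as the day of the surge, which is the most favourable case. The first-visit anchor is too early when 14 − S < R, that is S > 14 − R:
- R = 10: surge 5 or more days after the first visit.
- R = 12: surge 3 or more days after.
- R = 14: surge 1 or more days after.

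The plan gives no distribution for S, so no probability follows.

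**The case against.** The best answer is that sensible sites would not go wrong. The instruction to wait is given at the follow-up visit, so counting forward from that visit is natural. On the first-visit anchor the wait would be only 0 to 4 days, and nil for a day-14 repeat. The two sections can also be reconciled. Where the plan clearly waives menses, 7.3 says to begin immediately. For ovulatory women it says only that they may begin, which can be read as stating the test requirement while 4.2 supplies the start day. The tablet labels (cycle days 3 to 7) and the mention of menses in the check-in heading fit that. Finally, harm needs several things together: late ovulation, conception, no bleed, the first-visit anchor, 7.3 read without 4.2, and a false-negative test.

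Much of this stands as a reason to think the event uncommon. It does not settle the text. Nothing in 7.3 makes menses a condition, and the same section uses the visit's name for the first visit.

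Four stronger readings are tempting and are not supported:
- *All ovulatory women are tested too early.* Those ovulatory at the first visit test at 20 to 23 days after the surge. For them only the disagreement over menses remains.
- *The schematic sides with 7.3.* Its general check-in box does allow a start without menses. For late ovulators it probably agrees with 4.2, although its text is out of order in the available copy.
- *A stated share of late ovulators would be tested too early.* That would need the timing of the surge relative to a repeat drawn at a fixed interval, and a test detection limit. The documents give neither.
- *Menses must be required of every ovulatory woman.* Section 4.1.1 values not waiting for menses, so for women ovulatory at the first visit this is a trade-off.

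**Conclusion.** The point holds for women ovulatory only on the 10 to 14 day or LH-timed repeat. For them, 7.3 lets a raised-dose course start without menses, against 4.2 item 2a and probably the schematic; 4.1 is compatible with 4.2. Read literally, the two-week clock puts the pregnancy test 0 to 4 days after a 10 to 14 day draw and no more than 14 days after any surge that followed the first visit. That may be too early to exclude a conception from that ovulation. On the follow-up-visit reading the timing is adequate and only the conflict over menses remains.

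The day counts rest on the plan's own intervals. Whether the test is too early rests on the assumed reliability of a home test and on when the surge occurred. Frequency is unknown and the primary outcome is not affected. The wording should be fixed because it bears on drug exposure in early pregnancy and is cheap to change.

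**What to change.** Amend 4.2, 7.3 (cycles 1 and 2) and Appendix A:

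1. Time the no-menses pregnancy test at two weeks after the progesterone draw that showed ovulation, in place of two weeks after an unspecified midluteal visit.
2. For women ovulatory only on the repeat draw, make 7.3 match 4.2 item 2a: start with menses, after a negative test.
3. For women ovulatory at the first visit, make 4.2 and 7.3 state the same rule. Whether that rule requires menses is the investigator's decision.

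The cost is a wording amendment. Compared with the first-visit reading, some late ovulators would start the next cycle up to about two weeks later, since the test moves by 10 to 14 days. That gives up a little of the time saving that 4.1.1 offers as a reason for the stair-step approach.
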